1.1 Background

This project seeks to compare the clinical performance and subjective acceptance of the Biofinity XR Toric Multifocal and the Proclear Toric XR Multifocal soft contact lenses (both CooperVision Inc.). CooperVision (CVI) is extending the power range of the commercially available Biofinity Toric silicone hydrogel contact lenses to include multifocals. The extended power range for Biofinity Toric for subjects requiring a multifocal product will be called Biofinity XR Toric Multifocal. The Proclear Toric XR Multifocal is an existing lens which will be used as the control lens.

1.3 Study objectives

This study aims to compare the clinical performance and subjective acceptance of the Biofinity XR Toric Multifocal and the Proclear Toric XR Multifocal soft contact lenses.

1.4 Study design

This will be a randomised, subject-masked, crossover, bilateral study, controlled by cross-comparison. Thirty subjects will use each lens type for two weeks in random sequence. Follow-up visits for each lens will be performed after two weeks of wear. Lenses will be worn on a daily wear basis.

1.5 Statistical considerations

The principal hypothesis to be tested in this work is that subjective scores and visual acuity for the lenses will be substantially equivalent.

[REDACTED]

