1.5.1 Power analysis

In order to determine the study sample size, power analysis was employed using subjective vision data from a previous clinical study. In order to achieve 80% power to detect a difference of 10 units for subjective vision (assuming an alpha of 0.05 and two-tailed paired analysis), 16 completing subjects are required. In order to achieve 80% power to detect a difference of half a line on a LogMAR chart (assuming an alpha of 0.05 and two-tailed paired analysis), 22 completing subjects are required. To allow for discontinuations, 30 subjects will be recruited.

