2.1 Subject selection

In this work up to 30 subjects will be recruited and enrolled.

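### The principal hypothesis is equivalence, but the stated 80% power at 16 and 22 completers is for detecting a difference, so it is not power to show equivalence

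*Combined protocol and SAP*

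**What the plan says.** Section 1.5 sets the hypothesis: "The principal hypothesis to be tested in this work is that subjective scores and visual acuity for the lenses will be substantially equivalent". A redacted block follows it.

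Section 1.5.1, which shows no redaction, gives the sample size. For the subjective endpoint: "In order to achieve 80% power to detect a difference of 10 units for subjective vision", with the condition "assuming an alpha of 0.05 and two-tailed paired analysis), 16 completing subjects are required". For acuity, the target is "80% power to detect a difference of half a line on a LogMAR chart", under the same alpha and the same two-tailed paired analysis, and the requirement is 22 completers. The SDs are not given; the stated basis is that "power analysis was employed using subjective vision data from a previous clinical study".

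On recruitment, 1.5.1 says "To allow for discontinuations, 30 subjects will be recruited", and section 2.1 says "In this work up to 30 subjects will be recruited and enrolled". Sections 2.1.1 and 2.2 provide for replacing subjects who consent but do not complete the dispensing visit, and those who fail the eligibility criteria.

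**The concern.** The hypothesis and the power statement answer different questions. The 80% in 1.5.1 is the probability of rejecting no difference when the lenses really differ by 10 units or half a line. A study whose hypothesis is equivalence needs the probability of concluding equivalence when the lenses are alike or nearly so. That depends on a margin, a confidence level and an assumed true difference, and none of these enters the power sentences.

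Two things are at stake. First, the completer numbers, and hence the 8 subjects left for discontinuations (30 − 22), are not calibrated to the hypothesis being tested. Second, a plan powered this way invites a non-significant paired test to be read as equivalence, and that reading becomes easier the less precise the data are.

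**Working it through.** **Inputs from the plan (1.5.1).** Differences of 10 units and half a line; two-sided alpha 0.05; paired analysis; 80% power; 16 and 22 completers; 30 recruited.

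**Assumptions not in the plan.** Half a line = 0.05 logMAR; equivalence margin M equal to the stated difference; true difference δ = 0; normally distributed paired differences; no period or carryover effect.

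**Step 1: the SDs behind 16 and 22.** The plan's figures cannot be reproduced independently, because no SD is given. They can only be inverted.
- Exact paired t power (noncentral t, n − 1 degrees of freedom) equals 80% at n = 16 when difference/SD = 0.749, so SD = 10/0.749 = 13.34 units. At n = 22 the ratio is 0.626, so SD = 0.05/0.626 = 0.0798 logMAR. These are the largest SDs for which the t calculation gives 16 and 22.
- Inverting at n − 1 gives the lower limits: 12.85 units and 0.0778 logMAR.
- The normal approximation, SD = difference × √n / (1.960 + 0.842), gives 10 × 4/2.802 = 14.28 units and 0.05 × 4.690/2.802 = 0.0837 logMAR.

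The ranges carried forward are 12.9–14.3 units and 0.078–0.084 logMAR.

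**Step 2: power for an equivalence rule.** Conclude equivalence if |mean paired difference| + t × s/√n < M, where t is the 0.95 quantile (90% CI) or the 0.975 quantile (95% CI) on n − 1 degrees of freedom. This is two one-sided tests. With true paired SD σ, power is the integral over u, a chi-square variable on n − 1 degrees of freedom, of

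Φ[(h − δ)/(σ/√n)] − Φ[(−h − δ)/(σ/√n)], with h = max(0, M − t·σ·√(u/(n − 1))/√n).

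A rough check that treats σ as known, for acuity at n = 22 and σ = 0.0798:
- The standard error is 0.0798/4.690 = 0.0170.
- The 90% half-width is 1.721 × 0.0170 = 0.0293, which leaves 0.0207, or 1.22 standard errors. Power is about 2Φ(1.22) − 1 = 0.78 (exact 0.769).
- The 95% half-width is 2.080 × 0.0170 = 0.0354, which leaves 0.0146, or 0.86 standard errors. Power is about 0.61 (exact 0.600).

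**Step 3: exact results, in order of low / middle / high SD.**

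| Endpoint | Quantity | 90% CI rule | 95% CI rule |
|---|---|---|---|
| Acuity | power at 22 | 0.796 / 0.769 / 0.713 | 0.640 / 0.600 / 0.525 |
| Acuity | power at 30 | 0.927 / 0.912 / 0.879 | 0.851 / 0.825 / 0.770 |
| Acuity | completers for 80% | 23 / 24 / 26 | 28 / 29 / 32 |
| Subjective | power at 22 | 0.940 / 0.921 / 0.874 | 0.871 / 0.836 / 0.759 |
| Subjective | power at 30 | 0.988 / 0.982 / 0.964 | 0.969 / 0.955 / 0.919 |
| Subjective | completers for 80% | 16 / 17 / 19 | 20 / 21 / 24 |

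The row to read is 22 completers, because the same subjects supply both endpoints and acuity sets the requirement.

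**Step 4: the allowance out of 30 for acuity.** As planned it is 30 − 22 = 8. Under the 90% rule it is 30 − 23, 30 − 24 or 30 − 26, that is 7, 6 or 4. Under the 95% rule it is 2, 1 or none (32 exceeds 30).

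**Illustration only.** With a true acuity difference of 0.0125 logMAR (a quarter of the assumed margin) and 30 completers, power is 76–82% (90% rule) or 64–71% (95% rule). A margin tighter than half a line would also lower the figures. Neither input comes from the plan.

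**The case against.** The best defence is that difference sizing and equivalence sizing share the same paired SD and standard error, so 1.5.1 does bear on equivalence. At 22 completers the acuity half-width is about 0.029 (90%) or 0.035 (95%), inside half a line. In the simplest case (90% rule, margin equal to the stated difference, no true difference) acuity needs 23–26 completers rather than 22, and 30 covers that if enough of them finish. Replacement under 2.1.1 and 2.2 may mean that the allowance has to absorb only later losses, although how replacement fits the limit of 30 in 2.1 is not spelled out. All of this stands, and it limits the consequence. It does not turn the stated 80% into power for the hypothesis.

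Three stronger readings are tempting, and the documents support none of them:
- **That 30 subjects are too few.** This follows only from a stricter rule, a tighter margin or a non-zero true difference chosen by the reader.
- **That the subjective endpoint is underpowered because 16 completers fall short.** The study does not plan to stop at 16; at 22, subjective power is 87–94% under the 90% rule.
- **That the plan has no margin or decision rule.** Text after the hypothesis in 1.5 is redacted and may contain one. Even so, it would not change the complete power sentences in 1.5.1.

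**Conclusion.** The mismatch is certain: equivalence is the hypothesis, and the 80% is for detecting a difference. Its size is conditional. On the assumptions listed, acuity power at 22 falls from the nominal 80% to 71–80% (90% rule) or 52–64% (95% rule), and the acuity allowance falls from 8 to 4–7 or 0–2. Subjective power at 22 is 87–94% or 76–87%. With all 30 completing, acuity power is 88–93% or 77–85% and subjective power is 96–99% or 92–97%. The shortfall at the stated requirement therefore runs from almost nil to substantial. Which case applies cannot be read from 1.5.1. The point should be corrected, but it is not evidence that the study is too small.

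**What to change.** Keep recruitment at 30. In 1.5.1, replace the difference-test power with power for the equivalence rule, for each powered endpoint. A form for the sponsor to complete:

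*Equivalence is concluded only if the [level]% confidence interval for the mean paired lens difference lies within ±[margin]. With a paired SD of [value, from the previous study] and an assumed true difference of [value], [n] completers give 80% power; recruiting 30 leaves [30 − n] for discontinuations.*

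The margins are the sponsor's choice; the 10 units and half line already in 1.5.1 are natural candidates. Use the actual SDs, not the back-calculated ones above. If n exceeds 30, state instead the power at 30 and at the expected number of completers. Keep the rule consistent with any rule in the redacted part of 1.5, and say that a non-significant difference will not be taken as equivalence.

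The cost is a rewrite of one paragraph and a commitment to a margin, confidence level and assumed true difference. The stated acuity requirement may rise (to 23–26 or 28–32 on the assumptions here), and the allowance for discontinuations shrinks or disappears. Visits, lenses and recruitment are unchanged.

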3.2.3 Two-week follow-up/dispensing 2 visit

Subjects should attend wearing the study lenses which should have been in situ for at least two hours. Subjects who attend without lenses in situ for at least two hours will usually be rescheduled. The following procedures will be performed:

1. Lens wearing time on study visit day will be recorded.
2. Any study products relating to the previous two weeks of the study will be collected.
3. Details of the contact lens wear since the previous visit will be recorded (including wear time and comfortable wear time).
4. The subject will be asked to score the following with reference to appropriate visual analogue scales (0-100) as outlined in the 'Subjective ratings' document in [REDACTED]
[REDACTED]

[REDACTED]

[REDACTED]

- ∞ Overall comfort
- ∞ Dryness during the day

[REDACTED]

- ∞ Visual fluctuation/stability

[REDACTED]

[REDACTED]

- ∞ Overall handling
- ∞ Overall satisfaction
- ∞ Distance vision
- ∞ Intermediate vision
- ∞ Near vision
- ∞ Near vision in dim illumination

- ∞ Ghosting at distance

- ∞ Ghosting at near

- ∞ [REDACTED]

- ∞ Vision whilst driving during the day

- ∞ Vision whilst driving at night

- ∞ [REDACTED]

[REDACTED]

[REDACTED]

[REDACTED]

[REDACTED]

[REDACTED]

[REDACTED]

[REDACTED]

[REDACTED]

[REDACTED]

[REDACTED]

[REDACTED]

[REDACTED]

[REDACTED]

[REDACTED]

- 6. High illumination, high and low contrast distance and near (40 cm) monocular and binocular visual acuity will be recorded using distance and near logMAR charts before over-refraction. The range of clear vision at near (binocularly) will also be recorded for high contrast measures.
- 7. High illumination, binocular high contrast near visual acuity will be recorded at the subject's habitual working distance (which was recorded at the initial visit) using a near logMAR chart.
- 8. Spherical over-refraction will be performed on each eye if binocular distance high contrast visual acuity is less than 0.2. High illumination, high and low contrast distance and near (40 cm) monocular and binocular visual acuity will be recorded using distance and near logMAR charts. The range of clear vision at near (binocularly) will also be recorded for high contrast measures.

[REDACTED]

[REDACTED]

[REDACTED]

- 11. Lens rotation and stability will be recorded.
- 12. Lens fit and surface will be recorded as described in Section 3.2.1.

[REDACTED]

[REDACTED]

[REDACTED]

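### Does sizing on one subjective score and one acuity measure undercut a principal hypothesis about scores and acuity in general?

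*Combined protocol and SAP*

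**What the plan says.** Section 1.5 gives one principal hypothesis: "subjective scores and visual acuity for the lenses will be substantially equivalent". The visible sentence names two domains but no particular score, eye, distance, contrast or margin, and no rule for combining results. A redacted block follows it directly.

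Section 1.5.1 makes two separate calculations, each "assuming an alpha of 0.05 and two-tailed paired analysis":

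- "80% power to detect a difference of 10 units for subjective vision", for which "16 completing subjects are required";
- "80% power to detect a difference of half a line on a LogMAR chart", for which "22 completing subjects are required".

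Thirty are to be recruited to cover losses.

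At follow-up, section 3.2.3 (step 4) collects a set of 0-100 ratings, of which 13 are legible and others are blacked out. Step 6 adds a grid of acuities: "High illumination, high and low contrast distance and near (40 cm) monocular and binocular visual acuity will be recorded". Step 7 adds near acuity at the habitual working distance. Section 3.2.4 repeats these for the second lens.

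**The concern.** The hypothesis is worded in the plural, while the sizing takes one quantity from each domain. None of the legible ratings in section 3.2.3 is called simply subjective vision, and section 1.5.1 does not say which logMAR measure was sized, so neither calculation can be tied to a single listed item.

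Two things would be at stake. If every measure had to agree, a trial of two identical lenses could easily fail on one of them by chance. If the report could choose which measures count, the conclusion could be picked after the results were seen. In either case 80% would misdescribe the chance of reaching the principal conclusion.

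**Working it through.** **Inputs.** From section 1.5.1: differences of 10 units and half a line, two-sided alpha 0.05, paired analysis, 80% power, 16 and 22 completers, 30 recruited. Half a line is taken as 0.05 logMAR (assumption: one line is 0.1 logMAR). No standard deviation of the paired difference is given, so the stated sample sizes cannot be reproduced, only inverted.

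**Step 1: implied standard deviations.** Paired t-test power is P(T > t(0.975, n−1)), where T is noncentral t with n−1 degrees of freedom and noncentrality d√n/σ. Setting it to 80%:

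- n = 16, d = 10: σ = 13.34 units (down to 12.85 if 16 is the first integer to reach 80%).
- n = 22, d = 0.05: σ = 0.0798 logMAR (down to 0.0778 on the same reasoning).

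The upper ends are used below.

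**Step 2: power for the two sized measures.**

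| Completers | Subjective vision (noncentrality) | Acuity (noncentrality) | Both, if independent |
|---|---|---|---|
| 22 | 91.8% (10×√22/13.34 = 3.52) | 80.0% (0.05×√22/0.0798 = 2.94) | 0.918 × 0.800 = 73% |
| 30 | 97.8% (10×√30/13.34 = 4.11) | 91.2% (0.05×√30/0.0798 = 3.43) | 0.978 × 0.912 = 89% |

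The larger of the two sample sizes governs, so the subjective measure has well over 80% power at 22.

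**Step 3: count of visible measures.** Scores: 13. Acuities before over-refraction: 2 contrasts × 2 distances × 3 (right, left, binocular) = 12, plus 1 at habitual distance, gives 13. Total 26. If monocular acuity counts once: 2 × 2 × 2 + 1 = 9, total 22. Section 3.2.2 has ocular measurements made on each eye, but no visible text says the eyes are analysed as separate outcomes.

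**Step 4: the broad readings.** Suppose equivalence were judged by the absence of any significant difference. With identical lenses and independent measures, the chance of at least one false difference is 1 − 0.95^26 = 74%, or 1 − 0.95^22 = 68%. By simulation for 26 measures at 22 completers, it falls to 49% at a common correlation of 0.5 and 25% at 0.8.

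Suppose instead every measure had to pass two one-sided tests at 0.05, with margins of ±10 units and ±0.05 logMAR, a true difference of zero and the Step 1 standard deviations applied throughout. The chance that all pass is then as follows (exact product at correlation 0, 10,000 simulated trials otherwise):

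| Correlation | 26 measures, n = 22 | 26 measures, n = 30 | 22 measures, n = 22 | 22 measures, n = 30 |
|---|---|---|---|---|
| 0 | 1% | 24% | 3% | 34% |
| 0.3 | 3% | 33% | 7% | 44% |
| 0.5 | 9% | 47% | 15% | 53% |
| 0.8 | 36% | 69% | 41% | 73% |

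For one score plus one acuity under the same test: 0.921 × 0.769 = 71% at 22 and 0.982 × 0.912 = 90% at 30. About 26 completers give 80%. The single acuity measure alone has 77% at 22, so part of the gap below 80% comes from replacing a difference test with an equivalence test, not from the number of measures.

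**Step 5: what Step 4 assumes.** The all-must-agree rule, the use of the stated differences as margins, the standard deviations for comfort, handling, ghosting and low-contrast acuity, and the common correlation are all supplied from outside the visible text.

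**The case for a change.** The best case for acting is that single-measure power never carries over to a conclusion about two families of measures, and every 22- or 26-measure equivalence case in the table is below 80% even if all 30 subjects complete. Even the narrowest two-measure reading is below 80% at 22 completers. The visible parts of sections 2.9, 3.4 and 4.1 on data handling, missing data and reporting give no combination rule. Naming the principal measures would add no subjects or visits.

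The arithmetic stands, and so does the observation that 80% is a per-measure figure. The inference to a defect does not. The hypothesis does not say that all or each of the measures must agree, and taking one quantity from each named domain is at least as natural a reading as a conjunction of 26. Because text is redacted immediately after the hypothesis, the absence of a named measure or rule cannot be asserted. The lowest probabilities need independence, which is implausible for monocular and binocular acuity, or for overlapping vision ratings, in the same subjects. At 30 completers and correlations of 0.5 to 0.8 the 26-measure figure is 47% to 69%, so near-certain failure is not shown even under the strictest rule.

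There is also no neutral choice to substitute. The documents do not say which acuity was sized, and making distance acuity the sole acuity measure for a toric multifocal lens is a choice on which reasonable statisticians would differ.

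**Conclusion.** No change to the plan follows. Section 1.5.1 attaches 80% to each named difference separately, and no stated figure is shown to be wrong. What remains is detail not visible in the public text: which score and which acuity lead, and whether both must be met. The redacted block may supply it. If it does not, an analyst would sensibly lead with the sized quantities and report the other scores and acuities as estimates with confidence intervals.

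On that reading the sample is adequate: about 73% power to detect both stated differences at 22 completers and 89% at 30, with losses of up to 8/30 = 26.7% separating the two. These figures rest on standard deviations back-solved from the stated sample sizes, on 0.1 logMAR per line and on independence of the two measures. They are illustrations, not corrections. Whether power to detect a difference is the right basis for an equivalence hypothesis is a separate question, not decided here.

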1.5.1 Power analysis

In order to determine the study sample size, power analysis was employed using subjective vision data from a previous clinical study. In order to achieve 80% power to detect a difference of 10 units for subjective vision (assuming an alpha of 0.05 and two-tailed paired analysis), 16 completing subjects are required. In order to achieve 80% power to detect a difference of half a line on a LogMAR chart (assuming an alpha of 0.05 and two-tailed paired analysis), 22 completing subjects are required. To allow for discontinuations, 30 subjects will be recruited.

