2.7 Study control

This study is controlled by cross-comparison. Bias will be minimised by randomising the order of assessment.

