- 15. An overall grade for lens fit acceptance will be provided for both general lens fit and toric lens fit measures using the grading scales [REDACTED].

[REDACTED]

[REDACTED]

[REDACTED]

[REDACTED]

[REDACTED]

[REDACTED]

[REDACTED]

[REDACTED]

[REDACTED]

[REDACTED]

[REDACTED]

[REDACTED]

[REDACTED]

[REDACTED]

[REDACTED]

[REDACTED]

[REDACTED]

[REDACTED]

[REDACTED]

[REDACTED]

[REDACTED]

[REDACTED]

18. The lenses will then be removed and discarded.
19. Slit lamp biomicroscopy will be carried out, as detailed in section 3.2.1. The presence of any adverse events will be recorded [REDACTED]
20. The second lens pair will be applied (according to the randomisation table). The subject will be masked from the lens type, but will apply the lenses themselves without taking note of the position of any visible markings.
21. The steps outlined in Section 3.2.1, 13-25 will be repeated.
22. A new bottle of solution and a new case will be issued.
23. The subject will be discharged and asked to return for the four-week follow-up visit. Subjects should be asked to wear their lenses for a minimum of six hours per day, five days per week and to have worn lenses for at least two hours prior to attending the next scheduled visit.

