3.4 Missing, unused and spurious data

The absence of any data will be carefully and critically considered. If appropriate, partial datasets will be included in the final analysis. Any data missing from a subject visit will be outlined in the report by indicating the number of subjects included for each analysis. Data that are unused or considered to be spurious will be detailed and discussed in the report.

Section 4. Study co-ordination

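### Does the plan compare the two lenses with a plain paired test that ignores period effects?

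*Combined protocol and SAP*

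**What the plan says.** Section 1.4 sets the design: "This will be a randomised, subject-masked, crossover, bilateral study, controlled by cross-comparison". It continues: "Thirty subjects will use each lens type for two weeks in random sequence". Section 1.5 gives the aim: "The principal hypothesis to be tested in this work is that subjective scores and visual acuity for the lenses will be substantially equivalent". The text that follows this sentence is redacted.

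Section 1.5.1 sizes the trial. It asks for "80% power to detect a difference of 10 units for subjective vision", which needs 16 completers, and the same power for half a logMAR line, which needs 22. Both calculations are made "assuming an alpha of 0.05 and two-tailed paired analysis". Thirty are recruited to cover losses.

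Section 2.7 adds: "Bias will be minimised by randomising the order of assessment". Sections 3.2.2 (step 13) and 3.2.3 (step 20) assign the first and second lens pairs from a randomisation table; text beside the first mention is redacted. On incomplete data, Section 3.4 says: "If appropriate, partial datasets will be included in the final analysis". Section 2.9 says only that the data go to a statistical package.

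**The concern.** A crossover can carry a period effect: scores may differ between the first and second fortnight whichever lens is worn. Two features make one conceivable here. Wearers may adapt to multifocal toric lenses, and at the two-week visit the second pair goes in after the first is removed, with no washout.

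Randomising the order makes such an effect cancel on average, but does not remove it from a given dataset. A paired test without a period term then has two weaknesses. With equal sequences the effect inflates the variance of the within-subject differences and widens the interval. With unequal sequences it also shifts the estimated lens difference. Either would matter for a claim that two lenses are equivalent. A plain paired difference also cannot use a subject with follow-up on one lens only. Since the visible text names a paired analysis and never mentions period, sequence or balance, a reader may conclude that the plan has overlooked all this.

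**Working it through.** **1. What the phrase governs.** The word paired, as a type of analysis, appears only in Section 1.5.1, as an input to the sample size. No visible section names the final test or model. The natural place for it is Section 1.5, after the hypothesis, and that text is blacked out. The balance of the sequences would be described with the randomisation table, where text is also blacked out. Nor does the word exclude a period term: a within-subject model with lens and period effects is also a paired analysis.

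**2. Is the sizing harmed?** No standard deviation (SD) is stated, so 16 and 22 cannot be reproduced independently. I take half a line as 0.05 logMAR (assumption: one line is 0.1). Solving the noncentral t for the SD of paired differences that makes each n the smallest reaching 80% gives 12.85 to 13.34 units and 0.0778 to 0.0798 logMAR. At the upper values, a period term (error degrees of freedom n−2 instead of n−1) gives:

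| Endpoint | Power at stated n: without / with | n for 80% with term | Power at 30: without / with |
|---|---|---|---|
| 10 units, n = 16 | 80.0% / 79.6% | 17 | 97.8% / 97.7% |
| 0.05 logMAR, n = 22 | 80.0% / 79.8% | 23 | 91.2% / 91.2% |

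The cost is one subject, within the 30 recruited. Sizing by a paired test therefore says nothing against a period-adjusted final analysis.

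**3. If the final test were plain, with equal sequences.** Let P be the period 1 minus period 2 effect. The SD of differences becomes √(SD² + P²·n/(n−1)), and the 95% half-width is t(0.975, n−1) times that SD over √n. For n = 22 and P = 0.025: √(0.0798² + 0.025²×22/21) = 0.0838, and 2.080 × 0.0838/√22 = 0.0372. The documents give no P, so the table uses a quarter, half and all of the target. Plain-test power is from 40,000 simulated trials per row.

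| P (logMAR) | n = 22: half-width, power | n = 30: half-width, power |
|---|---|---|
| 0 | 0.0354, 80.2% | 0.0298, 91.4% |
| 0.0125 | 0.0358, 79.5% | 0.0302, 90.9% |
| 0.025 | 0.0372, 77.2% | 0.0313, 89.5% |
| 0.05 | 0.0420, 67.9% | 0.0353, 83.8% |
| With period term, any P | 0.0355, 79.8% | 0.0299, 91.2% |

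With 15 per sequence and P at half the target, the plain test rejects a true null 3.6 to 4.0% of the time across the two endpoints. It is conservative, so the loss is precision.

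**4. If the sequences were unequal.** With a and b completers per sequence, the paired mean is shifted by P(a−b)/(a+b). For P = 0.025:
- 12/10: 0.025 × 2/22 = 0.0023 logMAR
- 18/12: 0.025 × 6/30 = 0.005 logMAR, a tenth of the target
- 20/10: 0.025 × 10/30 = 0.0083 logMAR

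Across the two endpoints, with P at half the target, type I error is 5.3 to 5.4% at 18/12 and 7.5 to 8.4% at 20/10.

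**5. How likely is a large P?** The documents also contain points against one. Section 2.1.3 admits only subjects who completed the preceding study that fixed their lenses (criterion 4) and who have worn soft lenses successfully in the last two years (criterion 10). Follow-up outcomes are taken after about two weeks on each lens, which allows time to adapt. None of this rules out a period effect, but nothing suggests one as large as the target. The missing washout is mainly a carry-over matter: carry-over equal for both lenses acts like a period effect, while unequal carry-over would not be removed by a period term.

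**6. Subjects with one lens only.** The sizing is in completers, with room for 30 − 22 = 8 losses (26.7%). Sections 2.1.1 and 3.4 already provide for including all subject data and, where appropriate, partial datasets, with the number analysed reported. How these enter the comparison belongs to the unseen model. The calculations above use complete pairs and show no gain from single-lens data.

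**The case for a change.** The strongest reply is that the mechanism is real and the remedy cheap. The shift P(a−b)/(a+b) and the variance inflation are both correct. Sequences can finish unequal through dropout even if allocated equally. An equivalence claim depends on an unshifted estimate and a narrow interval. A period term costs one error degree of freedom, so it could be recommended on condition that the redacted text does not already include it.

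The mechanism and the arithmetic stand, and modelling period is good crossover practice. What does not stand is the step to a defect in this plan. The condition concedes that no omission has been shown; it asks for confirmation of text that exists but is hidden. Nor is the remedy free in every case. If allocation were unblocked (an assumption) and P were zero, average acuity power at 22 completers would be 77.7% with the term against 79.9% without. At P = 0.025 the order reverses: 77.8% against 76.2%. Which is better depends on a period effect and an allocation scheme that are not visible.

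**Conclusion.** The concern does not hold. The phrase it rests on is a sample-size assumption that fits a period-adjusted model as well as a plain test. The places where the final model and the sequence balance would be stated are redacted, and what is blacked out cannot be counted as absent. No visible rule in the plan gives a wrong result.

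The sizing is sound under either model, at a cost of one subject. If the final test did prove to be plain, a period effect of a quarter of the target would cost about half a percentage point of acuity power or less with equal sequences. A serious loss needs a period effect near the full 0.05 logMAR, or completing sequences as uneven as 20/10. These sizes rest on SDs back-solved from the stated power, on half a line being 0.05 logMAR, and on assumed values of P. The conclusion about the plan does not depend on them.
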